## 5 Reporting of Adverse Events

### 5.1 Definitions

An AE is defined as any untoward medical occurrence in a patient or clinical trial subject administered a medicinal product and which does not necessarily have a causal relationship with this treatment. Adverse events would not include information recorded as complications at screening (for new subjects) or baseline (for rollover subjects) for preplanned procedures for which the underlying condition was known and no worsening occurred. For rollover subjects, AEs that occurred during the double-blind trial (331-102-00058) and persist without recovery or resolution, but have not become exacerbated, will not be counted as AEs occurring in this trial. An adverse drug reaction is any untoward and unintended response to an IMP related to any dose administered.

A suspected adverse reaction is any AE for which there is a reasonable possibility that the IMP caused the AE.

An SAE includes any event that results in any of the following outcomes:

- Death
- Life-threatening; ie, the subject was, in the opinion of the investigator, or subinvestigator at immediate risk of death from the event as it occurred. It does not include an event that, had it occurred in a more severe form, might have caused death.
- Persistent or significant incapacity/disability or substantial disruption of the ability to conduct normal life functions.
- Requires inpatient hospitalization or prolongs hospitalization
  - Hospitalization itself should not be reported as an SAE; whenever possible the reason for the hospitalization should be reported.
  - Hospitalizations or prolonged hospitalizations for social admissions (ie, those required for reasons of convenience or other nonmedical need) are not considered SAEs.
- Congenital anomaly/birth defect.
- Other medically significant events that, based upon appropriate medical judgment, may jeopardize the subject and may require medical or surgical intervention to prevent one of the outcomes listed above, eg, allergic bronchospasm requiring intensive treatment in an emergency room or home, blood dyscrasias or convulsions that do not result in hospitalization, or the development of drug dependency or drug abuse.

Nonserious AEs are all AEs that do not meet the criteria for a “serious” AE.

Immediately Reportable Event (IRE):

- Any SAE
- Any AE related to occupational exposure.
- Potential drug-induced liver injury (DILI) (see [Section 5.4](#)).

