- Pregnancies are also defined as IREs. Although normal pregnancy is not an AE, it will mandate IMP discontinuation and must be reported on an IRE form to the sponsor. Pregnancy will only be recorded in the source documents and the AE Section of the CRF if there is an abnormality or complication. This applies both to pregnancies of subjects and pregnancies of subjects' partners.

Clinical Laboratory Assessment Value Changes: It is the investigator's or subinvestigator's responsibility to review the results of all laboratory tests as they become available. This review will be documented by the investigator's or subinvestigator's dated signature on the laboratory report. For each abnormal laboratory test result, the investigator or subinvestigator needs to verify whether this is an abnormal (ie, clinically relevant) change from baseline for that individual subject. This determination, however, does not necessarily need to be made the first time an abnormal value is observed. The investigator or subinvestigator may repeat the laboratory test or request additional tests to verify the results of the original laboratory tests. If this laboratory value is considered medically relevant by the investigator or subinvestigator (subject is symptomatic, requiring corrective treatment or further evaluation), or if the laboratory value leads to discontinuation or meets the criteria for an SAE, this is considered an AE.

Severity: Adverse events will be graded on a 3-point scale and reported. The intensity of an AE is defined as follows:

**1 = Mild:** Discomfort noticed, but no disruption to daily activity.

**2 = Moderate:** Discomfort sufficient to reduce or affect normal daily activity.

**3 = Severe:** Inability to work or perform normal daily activity.

IMP Causality: Assessment of causal relationship between an AE and the IMP:

**Related:** There is a reasonable possibility of a temporal and causal relationship between the IMP and the AE.

**Not related:** There is no temporal or reasonable relationship between the IMP and the AE.

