If a subject is suspected to be pregnant before she receives IMP, the IMP administration must be withheld until the results of pregnancy tests are available. If the pregnancy is confirmed, the subject must not receive the IMP and must not be enrolled in the trial. If pregnancy is suspected while the subject is taking IMP, the IMP must be withheld immediately (if reasonable, taking into consideration any potential withdrawal risks) until the result of the serum pregnancy test is known. If pregnancy is confirmed, the IMP will be permanently discontinued in an appropriate manner (eg, dose tapering if necessary for subject safety) and the subject will be withdrawn from the trial.

The investigator or subinvestigator must immediately notify the sponsor of any pregnancy associated with IMP exposure during the trial and for 30 days after the last dose of IMP, and record the event on the IRE form, and forward it to the sponsor. The sponsor will forward Pregnancy Surveillance Form(s) for monitoring the outcome of the pregnancy.

Protocol-required procedures for trial discontinuation and follow-up must be performed on the subject unless contraindicated by pregnancy (eg, x-ray studies). Other appropriate pregnancy follow-up procedures should be considered, if indicated. In addition, the investigator or subinvestigator must report to the sponsor, on appropriate Pregnancy Surveillance Form(s), follow-up information regarding the course of the pregnancy, including perinatal and neonatal outcome. Infants will be followed for a minimum of 6 months from the date of birth.

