### **5.7.2 Follow-up of Serious Adverse Events and Immediately Reportable Events**

This trial requires that subjects be actively monitored for SAEs and IREs up to 30 days ( $\pm 5$  days) after the final day of IMP administration (end of trial date [final day of observation]).

Serious AEs and IREs that are identified or ongoing at the end of trial date must be recorded in the source documents and the AE section of the CRF. Between the end of trial date for the individual subject and the end of trial date for the last subject, if any new information regarding an SAE or IRE becomes available (eg, the event is resolved), this must be reported to the sponsor using the IRE form and so on, and the information must be recorded in the source documents and the AE section of the CRF. The investigator or subinvestigator will follow SAEs and IREs, and will continue to report any significant information to the sponsor until the events are resolved or stabilized, or the subject is lost to follow-up or has died, using the IRE form and so on.

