10.2 Adverse Events

All adverse events (AEs) will be coded by Medical Dictionary for Regulatory Activities (MedDRA) (Ver. 24.0) System Organ Class (SOC) and Preferred Term (PT). Numbers and proportions of subjects with the following AEs will be summarized by SOC and PT. If an AE occurs more than once in the same subject, the severest event will be used in summarization.

- Adverse events occurring after initiation of IMP administration (treatment-emergent adverse events [TEAEs])
- TEAEs by severity
- TEAEs with an outcome of death
- Serious TEAEs
- TEAEs leading to discontinuation of the IMP
- TEAEs occurring in $\geq 2\%$ of subjects in any group
- TEAEs by date of initial onset (1-7, 8-14, 15-28, 29-56, 57-84, 85-112, 113-140, 141-168, 169-196, 197-224, 225-252, 253-280, 281-308, 309-336, 337-364, > 364 , post-trial treatment)

TEAEs potentially causally related to the IMP will also be summarized in the same manner.

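### Protocol 5.1 and 5.7.2 put a partner's pregnancy complication, and a normal pregnancy still continuing at the end of observation, into the subject's AE record, and 5.1 leaves unclear whether a partner's pregnancy affects treatment

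*Protocol*

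**What the plan says.** **Protocol 5.1** opens its definitions with "An AE is defined as any untoward medical occurrence in a patient or clinical trial subject administered a medicinal product". It then classes pregnancies as immediately reportable events (IREs). The pregnancy bullet makes three statements in sequence:

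- On status and treatment: "Although normal pregnancy is not an AE, it will mandate IMP discontinuation", with reporting to the sponsor on the IRE form.
- On the CRF, it sets a condition for entry in the AE section: "Pregnancy will only be recorded in the source documents and the AE Section of the CRF if there is an abnormality or complication". An uncomplicated pregnancy therefore stays out of that section.
- On whose pregnancies are meant, the bullet closes with one sentence: "This applies both to pregnancies of subjects and pregnancies of subjects' partners".

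**Protocol 5.7.2** monitors each subject for SAEs and IREs until 30 days (± 5 days) after the last IMP day. It then says, of SAEs and IREs together: "IREs that are identified or ongoing at the end of trial date must be recorded in the source documents and the AE section". It makes no exception for pregnancy.

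**Protocol 5.5** deals with a subject who is, or may be, pregnant before or while taking the IMP. In that context it says "If pregnancy is confirmed, the IMP will be permanently discontinued in an appropriate manner". It contains no stopping rule for a partner's pregnancy. The withdrawal list in **3.8.3.2** has pregnancy as item 6, does not say whose pregnancy, and refers to 5.5 and not to 5.1.

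**SAP 10.2** counts subjects with AEs that start after the first IMP dose, by SOC and PT. SAP 10.2.1 repeats this for AEs of interest and SAP 10.2.2 for subgroups, including sex. None of these sections sets aside partner events or normal pregnancies.

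**The concern.** An AE table should describe what happened to people who took brexpiprazole. Followed literally, these rules bring in two kinds of record that do not belong: an event in a partner who never received the product, and a normal pregnancy that the protocol itself says is not an AE. Both would be tabulated as the subject's TEAE, and some could fall into an AE-of-interest category. A normal pregnancy recorded with the IMP stopped could also be counted among TEAEs leading to discontinuation, although 3.8.3.2 lists pregnancy (item 6) separately from adverse events (item 1).

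The last sentence of the 5.1 bullet raises a second question, about conduct. It does not say how much of the bullet it extends to partners, and one of the statements above it concerns mandatory discontinuation.

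**Working it through.** Apart from the size estimate at the end, this is a comparison of texts.

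**1. Partner's complication.** The sentence extending the rule to partners directly follows the sentence on recording in the AE section. Whatever else it covers, it covers that one. So a partner's abnormality or complication goes into the AE section of the subject's CRF. The AE definition, however, covers "any untoward medical occurrence in a patient or clinical trial subject administered a medicinal product", and a partner is neither. Protocol 5.2 also asks, for every AE, for its relationship to the IMP and the action taken with the IMP. Neither item has a sensible answer for someone who was not dosed. The two parts of 5.1 do not fit together.

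**2. Normal pregnancy.**
- Under 5.1 a normal pregnancy is an IRE, is not an AE, and stays out of the AE section.
- Under 5.7.2 any IRE identified or ongoing at the end of trial date goes into the AE section.
- Protocol 3.7.9 defines the end of trial date by the last subject, but 5.7.2 equates it in parentheses with the final observation day, 30 − 5 = 25 to 30 + 5 = 35 days after the last dose. If the IMP is stopped when pregnancy is confirmed, a continuing pregnancy will usually still be ongoing then.

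For that case the two sections give opposite instructions. Protocol 5.3 does not settle it. It says the IRE form is not the AE section, but its follow-up paragraph then refers to SAEs and IREs collectively as AEs.

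**3. Treatment.** The closing 5.1 sentence has two readings.
- Broad: the whole bullet applies to partners, including IRE status, discontinuation, the form and recording. Then 5.1 requires something that 5.5 does not provide for.
- Narrow: only the recording sentence applies to partners. Then there is no conflict with 5.5, but 5.1 no longer clearly makes a partner's pregnancy an IRE.

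The text does not choose between them.

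**4. Where the entries would appear.** SAP Appendix 4 contains obstetric terms: eclampsia under seizures; HELLP syndrome and anaemia of pregnancy under haematopoietic events; obstetrical pulmonary embolism and venous thrombosis in pregnancy under VTE. A partner's eclampsia would be counted as the subject's seizure-related AE, and Protocol 1.3 names seizures as an important risk. In the by-sex tables a man could carry an obstetric term.

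**5. Size.** The documents give no number of pregnancies. I assume 0 to 3 entries in different subjects, and use 100 subjects as an illustrative denominator. The 100 in the protocol is the target for completers, so the safety set should be larger and the percentages smaller.

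- *PT or AE-of-interest row:* 1/100 = 1 percentage point per entry, so 0 to 3 points if all fall in one row.
- *Overall TEAE incidence:* an entry counts only if the subject has no other TEAE. With the 72.3% AE incidence of the overseas long-term MDD trial (Protocol 1.2.2.4) as illustration, and assuming independence, each entry adds on average 1 − 0.723 = 0.277 subjects. Three entries add 3 × 0.277 = 0.83 subjects, or about 0.8 points per 100.

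**The case against.** **The specific rule should prevail.** Section 5.1 is the rule written for pregnancy and says when it may be recorded; 5.7.2 is a general follow-up rule. A careful site would follow 5.1, and a normal pregnancy entered by mistake could be queried because it is not an AE by definition. This lowers the chance of wrong entries. It does not remove the conflict: 5.7.2 is mandatory, makes no exception, and SAP 10.2 describes no screening step.

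**Recording partner complications is the sponsor's choice.** The sponsor clearly wants these data, and 5.1 lists congenital anomaly or birth defect as an SAE outcome, so pregnancy outcomes already reach beyond the dosed person. The wish to collect them is sound. The difficulty is the place of recording, because the AE section feeds the TEAE tables. The IRE form and the Pregnancy Surveillance Forms in 5.5 already offer another route.

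**Nothing inferential depends on it.** SAP section 6 plans no primary or secondary outcome and the analyses are descriptive. An obstetric term against a man would be easy to notice. All of this stands and keeps the point minor.

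**The treatment conflict is only one reading.** This also stands. A reader might infer that 5.1 requires brexpiprazole to be stopped when a partner is pregnant. The documents do not establish that: the sentence's nearest antecedent is the recording rule, and 3.8.3.2 item 6 sends the site to 5.5, whose stopping text concerns the subject's own pregnancy.

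**Conclusion.** The recording problem is real on both counts. Protocol 5.1 conflicts with its own AE definition for a partner's complication, and with 5.7.2 for a normal pregnancy identified or ongoing at the end of trial date. On treatment, 5.1 is ambiguous: it can be read to extend mandatory discontinuation to partner pregnancies, and 5.5 has no such provision.

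Two further inferences go too far. Not every normal pregnancy is directed to the AE section, because 5.7.2 has its end-of-trial condition. Nor does every entry raise overall TEAE incidence; it does so only when the subject has no other TEAE.

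The effect runs in one direction and is small: one subject per entry in the affected PT or AE-of-interest row, and on the illustration above about 0.28 of a subject in overall incidence. This rests on an assumed 0 to 3 cases, a denominator of 100, and an AE incidence borrowed from another trial. The likely number of cases is very small, and no planned conclusion would change. It is a minor correction, worth making because rows for rare events are where a single misplaced entry shows.

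**What to change.** - **Protocol 5.7.2:** limit recording in the AE section to SAEs and to those IREs that meet the 5.1 AE definition in the trial subject. A normal pregnancy is then exempt, as 5.1 intends.
- **Protocol 5.1:** route partner pregnancies and their complications to the IRE form and the Pregnancy Surveillance Forms only, and state exactly what the closing sentence of the bullet covers.
- **SAP 10.2:** state that partner events and normal pregnancies are not counted as TEAEs. No new listing is needed. SAP Appendix 6 has only a pregnancy-test listing (LAB-5), and a separate listing of partner events would need a data source that the documents do not describe.
- **Treatment:** Protocol 5.1, 5.5 and 3.8.3.2 item 6 must be reconciled on whether a partner's pregnancy affects the subject's treatment. This review does not say which rule is right.

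The cost is a few sentences in the protocol and one in the SAP, with no new data. If the protocol can no longer be amended, the SAP sentence alone corrects the tables, provided that partner events already entered can be identified, for instance from the IRE forms.

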## 5.2 Eliciting and Reporting Adverse Events

The investigator or subinvestigator will periodically assess subjects for the occurrence of AEs. To avoid bias in eliciting AEs, subjects should be asked the nonleading question: “How have you felt since your last visit?” For all AEs (serious and nonserious) reported by the subject, the event name, start and stop dates, severity, seriousness, relationship to IMP, actions taken regarding IMP administration, and outcome thereof must be recorded in the source documents and CRFs provided by the sponsor. Adverse event and SAE collection is to begin after a subject has signed the ICF.

Use medical terminology in AE reporting. Adverse events should be reported as a single unifying diagnosis whenever possible or, in the absence of a unifying diagnosis, as individual signs or symptoms. Exacerbation or disease progression should be reported as an AE only if there are unusual or severe clinical features that were not present, or experienced earlier, or not expected based on the course of the condition. If a reported AE has worsened in severity or seriousness, it should be reported as a new AE on the CRF.

In addition, the sponsor must be notified immediately by e-mail, in principle, of any IREs according to the procedure outlined below, in [Section 5.3](#) Immediately Reportable Events. Special attention should be paid to recording hospitalization and concomitant medications.

## 5.3 Immediately Reportable Events

The investigator or subinvestigator must report any SAE, potential DILI, or confirmed pregnancy to the sponsor by e-mail (using the contact information on the title page of this protocol) immediately after either the investigator, subinvestigator, or designee becomes aware of the event. The IRE form and so on should be completed and sent by e-mail, in principle, to the sponsor. Please note that the IRE form is NOT the AE Section of the CRF. Due consideration must be given to privacy when the IRE form and so on is sent by mail or other means of communication.

For subjects experiencing SAEs or IREs, such AEs should be followed until the events are resolved or stabilized, or the subject is lost to follow-up or has died. *Resolved* means that the subject has returned to the baseline state of health, and *stabilized* means that the investigator or subinvestigator does not expect any further improvement or worsening of the subject’s condition. It is expected that the investigator or subinvestigator will provide or arrange appropriate supportive care for the subject and will provide prompt updates on the subject’s status to the sponsor.

## **5.4 Potential Drug-induced Liver Injury**

For a subject who experiences an elevation in aspartate aminotransferase (AST) or alanine aminotransferase (ALT) that is  $\geq 3$  times the upper limit of normal (ULN), total bilirubin level should also be evaluated. If the total bilirubin is  $\geq 2$  times the ULN, complete the IRE form and so on with all values listed and also report as an AE in the source documents and CRF.

## **5.5 Pregnancy**

Women of childbearing potential (WOCBP) are defined as female subjects for whom menstruation has started and who are not documented as sterile (ie, have had a bilateral oophorectomy and/or hysterectomy or who have been postmenopausal for at least 12 months).

For WOCBP and for men who are sexually active, there must be a documented agreement that the subject and/or their partner will take effective measures (ie, double-barrier method) to prevent pregnancy during the course of the trial and for 30 days after the last dose of IMP. Unless the subject or their partner is sterile (ie, women who have had a bilateral oophorectomy and/or hysterectomy or who have been postmenopausal for at least 12 consecutive months; or men who have had a bilateral orchidectomy) or remains abstinent, 2 of the following precautions must be used: vasectomy, tubal ligation, vaginal diaphragm, intrauterine device, oral contraceptives, or condom with spermicide. Any single method of birth control, including vasectomy and tubal ligation, may fail, leading to pregnancy. The contraceptive method will be documented at each trial visit.

Before enrolling WOCBP in this clinical trial, investigators or subinvestigators must review the below guidelines about trial participation with all WOCBP. The topics should generally include:

- General information
- Informed consent form
- Pregnancy prevention information
- Drug interactions with hormonal contraceptives
- Contraceptives in current use
- Guidelines for the follow-up of a reported pregnancy

Before trial enrollment, WOCBP must be advised of the importance of avoiding pregnancy during trial participation and the potential risk factors for an unintentional

pregnancy. The subject must sign an informed consent form stating that the above-mentioned risk factors and the consequences were discussed with her.

During the trial, all WOCBP should be instructed to contact the investigator or subinvestigator immediately if they suspect they might be pregnant (eg, missed or late menstrual cycle).

If a subject is suspected to be pregnant before she receives IMP, the IMP administration must be withheld until the results of pregnancy tests are available. If the pregnancy is confirmed, the subject must not receive the IMP and must not be enrolled in the trial. If pregnancy is suspected while the subject is taking IMP, the IMP must be withheld immediately (if reasonable, taking into consideration any potential withdrawal risks) until the result of the serum pregnancy test is known. If pregnancy is confirmed, the IMP will be permanently discontinued in an appropriate manner (eg, dose tapering if necessary for subject safety) and the subject will be withdrawn from the trial.

The investigator or subinvestigator must immediately notify the sponsor of any pregnancy associated with IMP exposure during the trial and for 30 days after the last dose of IMP, and record the event on the IRE form, and forward it to the sponsor. The sponsor will forward Pregnancy Surveillance Form(s) for monitoring the outcome of the pregnancy.

Protocol-required procedures for trial discontinuation and follow-up must be performed on the subject unless contraindicated by pregnancy (eg, x-ray studies). Other appropriate pregnancy follow-up procedures should be considered, if indicated. In addition, the investigator or subinvestigator must report to the sponsor, on appropriate Pregnancy Surveillance Form(s), follow-up information regarding the course of the pregnancy, including perinatal and neonatal outcome. Infants will be followed for a minimum of 6 months from the date of birth.

